6.7.1 Pulmonary Symptoms

If new or worsening pulmonary symptoms (e.g., dyspnea) or radiological abnormality suggestive of interstitial lung disease is observed, an interruption in AZD9291 dosing is recommended, and the AstraZeneca representative should be informed. It is strongly recommended to perform a full diagnostic workup, to exclude alternative causes such as lymphangitic carcinomatosis, infection, allergy, cardiogenic edema, or pulmonary hemorrhage.

Where ILD is suspected, administer corticosteroids at a dose of 1 to 2 mg/kg/day prednisone equivalents for Grade 2 or greater pneumonitis, followed by corticosteroid taper. Permanently discontinue for severe (Grade 3) or life-threatening (Grade 4) pneumonitis and withhold until resolution for moderate (Grade 2) pneumonitis.

In the absence of a diagnosis of interstitial lung disease AZD9291 may be restarted.

6.7.2 QTc Prolongation

Patients with QTcF prolongation fulfilling the following criteria (i.e., confirmed QTcF prolongation to > 500 msec absolute or a > 60 msec increase from baseline) should have AZD9291 interrupted and regular ECGs performed until resolution to baseline. If the toxicity does not resolve to < grade 1 within 3 weeks the patient will be permanently withdrawn from AZD9291 treatment.

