6.7 Management of IP related toxicities

Dose adjustment for adverse events should be in accordance with the following table:

Table 3. AZD9291 dose adjustment information for adverse reactions

Target Organ	Adverse Reactiona	Dose Modification
Pulmonary	ILD/Pneumonitis	Permanently discontinue AZD9291
Cardiac	QTc interval greater than 500 msec on at least 2 separate ECGs	Withhold AZD9291 until QTc interval is less than 481 msec or recovery to baseline if baseline QTc is greater than or equal to 481 msec, then restart at a reduced dose (40 mg). QTc interval prolongation with signs/symptoms of serious arrhythmia Permanently discontinue AZD9291
Other	Grade 3 or higher adverse reaction	Withhold AZD9291 for up to 3 weeks If Grade 3 or higher adverse reaction improves to Grade 0-2 after withholding of AZD9291 for up to 3 weeks AZD9291 may be restarted at the same dose (80 mg) or a lower dose (40 mg) Grade 3 or higher adverse reaction that does not improve to Grade 0-2 after withholding for up to 3 weeks Permanently discontinue AZD9291

a Note: The intensity of clinical adverse events graded by the National Cancer Institute (NCI) Common Terminology Criteria for Adverse Events (CTCAE) version 4.0.

If a patient experiences a CTCAE grade 3 or higher and/or unacceptable toxicity (any grade), where the clinician considers the event of concern to be specifically associated with AZD9291 (and not attributable to the disease or disease-related processes for which patient is being treated), dosing will be interrupted and supportive therapy administered as required in accordance with local practice/guidelines. Detailed information on the clinical management of events may be found in Appendix B, "Guidance for the Management of Adverse Events in Studies using 80mg AZD9291."

Patients with QTc prolongation (i.e., confirmed QTc prolongation to >500 msec absolute or a > 60

msec increase from baseline) should have AZD9291 treatment interrupted and regular ECGs performed until resolution to baseline.

If the toxicity resolves or reverts to \leq CTCAE grade 2 within 3 weeks of onset, treatment with AZD9291 may be restarted at the same dose (80 mg, daily) or a lower dose (40 mg, daily) using the rules below for dose modifications (Table 4). There will be no individual modifications to dosing schedule in response to toxicity, only potential dose reduction or dose interruption.

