If the toxicity does not resolve to \leq CTCAE grade 2 after 3 weeks, then the patient should be withdrawn from the study and observed until resolution of the toxicity.

Table 4. Dose Interventions

Intervention	AZD9291 Dose
Starting Dose	80 mg daily
Reduced Dose	40 mg daily

On resolution of toxicity within 3 weeks:

If an event subsequently requires dose interruption, AZD9291 may restart at the same dose or the reduced dose, on resolution/improvement of the event at the discretion of the clinician.

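### For QTc above 500 msec, Table 3, section 6.7.2 and the general text of 6.7 give different recovery tests, time limits and restart doses, and nothing says which governs

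*Combined protocol and SAP*

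**What the plan says.** Section 6.7 opens with "Dose adjustment for adverse events should be in accordance with the following table". In the cardiac row of Table 3 the trigger is "QTc interval greater than 500 msec on at least 2 separate ECGs" and the instruction is "Withhold AZD9291 until QTc interval is less than 481 msec", followed by a restart at 40 mg. (The row has a separate target for a baseline of 481 msec or more, which is not at issue here.) The row gives no maximum hold and no consequence for a patient who does not recover. The row labelled Other in the same table gives both: "Withhold AZD9291 for up to 3 weeks", then permanent discontinuation.

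Below the table, section 6.7 interrupts treatment for a confirmed QTc above 500 msec or a rise of more than 60 msec from baseline, with regular ECGs until return to baseline. The next paragraph covers toxicity in general. If it falls to grade 2 or lower within 3 weeks of onset, dosing may resume at 80 or 40 mg. If it does not, "then the patient should be withdrawn from the study and observed until resolution of the toxicity".

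Section 6.7.2 uses the same two QTcF triggers and the same ECG follow-up, and adds: "If the toxicity does not resolve to < grade 1 within 3 weeks the patient will be permanently withdrawn from AZD9291 treatment". It states no restart dose.

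**The concern.** These are re-dosing and stopping instructions for a cardiac toxicity, to be applied at about 10 sites. They differ on three things a site must decide: how far QTc has to recover, how long to wait, and at what dose to resume. Section 6.7 tells sites to follow the table, while 6.7.2 is the section written specifically for QTc prolongation. The protocol does not rank one above the other. Depending on the text a site follows, a slow recoverer could be exposed again after a QTc above 500 msec, possibly at full dose, or could permanently lose treatment.

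**Working it through.** No figure in the plan needs reproducing. The check sets the rules side by side for one event, a confirmed QTc above 500 msec.

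| Source | Recovery test | Time limit | Restart dose | If not recovered |
|---|---|---|---|---|
| Table 3, cardiac row | QTc below 481 msec | none stated | 40 mg | not stated |
| Section 6.7.2 | below grade 1 | 3 weeks | not stated | permanent withdrawal from treatment |
| Section 6.7, general text | grade 2 or lower | 3 weeks from onset | 80 or 40 mg | withdrawal from the study |

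Three patients, each held after a QTc above 500 msec, show where the rules part. Day 21 is 3 × 7 days.

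1. **QTc is 481 msec or more at day 21 and falls below 481 msec later.** The cardiac row read alone restarts at 40 mg. Section 6.7.2 has already stopped the patient permanently. This assumes that 481 msec or more is not below grade 1.
2. **QTc is below 481 msec by day 21 but the toxicity is not below grade 1.** The cardiac row has restarted the patient at 40 mg; section 6.7.2 requires permanent withdrawal; the general text would allow 80 or 40 mg if the grade is 2 or lower. The documents give no msec limits for the grades, so the width of this band cannot be stated.
3. **QTc is below 481 msec and the toxicity is below grade 1 within 21 days.** The cardiac row and 6.7.2 are both satisfied and the restart dose is 40 mg. The general text, applied to the same patient, would still allow 80 mg.

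The second trigger, a rise of more than 60 msec, appears in 6.7 and 6.7.2 but not in Table 3. In whole msec, more than 60 means at least 61.

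- The trigger can be met without exceeding 500 msec if baseline + 61 ≤ 500, so baseline ≤ 439 (439 + 61 = 500). Section 3.2 excludes only QTcF above 470 msec, so such patients are eligible. They can be held under the text without ever meeting the table's trigger.
- The trigger can be met while QTc is already below 481 msec if baseline + 61 ≤ 480, so baseline ≤ 419 (419 + 61 = 480). For these patients the 481 msec threshold alone cannot serve as the recovery test.

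**The case against.** The strongest reply is that a silent row does not permit an unlimited hold. Section 6.7.2 is headed for this toxicity and uses mandatory wording, and the general text of 6.7 also works to 3 weeks. A careful reader can follow the row and 6.7.2 together: hold, restart at 40 mg on recovery, and stop at 3 weeks otherwise. That reading is plausible and largely disposes of patient 1. It does not settle patient 2, because it leaves open whether below 481 msec or below grade 1 is the test. Nor does it exclude the 80 mg option in the general text. One can argue that a specific row overrides a general paragraph, but the protocol does not say so, and the paragraph makes no exception for QTc.

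Other points on that side stand. Prolongation with evidence of serious arrhythmia has its own unambiguous instruction in Table 3 to stop permanently. Section 3.2 excludes QTcF above 470 msec, QT-prolonging medication and other QT risk factors, so few patients may be affected. The return to baseline in 6.7 and 6.7.2 can be read as the length of ECG follow-up, so it is not counted here as a further restart test. The extra 60 msec trigger is an omission from the table, not a contradiction. Appendix B, which 6.7 cites for detailed management, was not available to check.

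**Conclusion.** The inconsistency is real and worth correcting. For one event the protocol states three recovery tests, a time limit in two places but not in the cardiac row, and two sets of restart doses, with no order of precedence. The disagreement over stopping is confined to patients not below grade 1 at 3 weeks. The disagreement over dose can reach anyone restarted after a QTc above 500 msec.

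A reader might infer more than the documents support:

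- That 6.7.2 stops every patient at 3 weeks. It stops only those whose toxicity has not resolved to below grade 1.
- That section 6.7 has no time limit for QTc events. Only the cardiac row lacks one.
- That a number of patients, or a msec range, can be attached to the problem. No event rate and no grade limits are given.
- That the efficacy result is compromised. The response endpoint, the sample size and the two-stage boundaries do not depend on these rules.

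The conclusion rests on the text of sections 6.7 and 6.7.2. Patient 1 also needs the assumption that 481 msec or more is not below grade 1.

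**What to change.** Keep the protocol's stricter stated rule and put it in the cardiac row of Table 3.

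- **QTcF above 500 msec on at least 2 ECGs:** withhold for up to 3 weeks. Restart only at 40 mg, and only if, within those 3 weeks, QTcF is below 481 msec and the toxicity has resolved to below grade 1. Otherwise discontinue osimertinib permanently.
- **Rise of more than 60 msec from baseline:** add it to the row as a hold trigger, with the same withdrawal rule if the toxicity is not below grade 1 within 3 weeks.
- **General rule:** state that the restart at grade 2 or lower, at 80 or 40 mg, does not apply after a QTc above 500 msec.
- **Cross-references:** make 6.7 and 6.7.2 refer to the row, say when the 3 weeks start, and check Appendix B against the new wording.

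The cost is a wording amendment, with no extra patients; an ECG by the end of week 3 falls under the regular ECGs already required. The downside is that some slow recoverers whom Table 3 alone would restart are permanently stopped, as 6.7.2 already requires. Sites also lose the option of resuming 80 mg after a QTc above 500 msec, which the cardiac row already does not offer.

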6.7.3 Corneal Ulceration

Patients experiencing corneal ulceration will not be permitted to restart AZD9291 treatment.

6.7.4 Skin reactions

Recommendations for appropriate management of skin reactions, including guidance on dose-adjustments for clinically significant and/or intolerable skin reactions that are considered by the clinician to be causally related to AZD9291 is provided in Appendix B, Guidance for the Management of Adverse Events in Studies using 80mg AZD9291."

6.7.5 Diarrhea

Recommendations for appropriate management of diarrhea, including dose-adjustments for adverse events of diarrhea that are of CTCAE grade ≥ 3 or that are clinically significant and/or intolerable and considered by the clinician to be causally related to AZD9291, is provided in Appendix B, "Guidance for the Management of Adverse Events in Studies using 80mg AZD9291."

6.8 Study governance and oversight

An Executive Steering Committee will be set up. It will involve experts with the relevant knowledge and experience required for the study. This Executive Committee will have the executive oversight and supervision of the study. It will also be involved in the publication strategy of the study.

7. INVESTIGATIONAL PRODUCT AND OTHER TREATMENTS

7.1 Identity of investigational product (AZD9291)

Investigational product	Dosage form and strength	Manufacturer
AZD9291	40mg Tablets	

80mg Tablets

AstraZeneca

AstraZeneca will supply AZD9291 as tablets for oral administration as a single daily dose of 80 mg. AZD9291 will usually be supplied as either bulk or unlabelled bottles for ISS/ESR studies. Additional information about the Investigational product may be found in the Investigators' Brochure.

7.2 Dose and treatment regimens

AZD9291 is administered as 80 mg once daily. AZD9291 can be taken without regard to food.

Doses should be taken approximately 24 hours apart at the same time point each day. Doses should not be missed. If a patient misses taking a scheduled dose, within a window of 12 hours, it is acceptable to take the dose. If it is more than 12 hours after the dose time, the missed dose should not be taken, and patients should be instructed to take the next dose at the next scheduled time. If a patient vomits after taking their AZD9291, they should not make up for this dose, but should take the next scheduled dose.

The dose of 80 mg AZD9291 daily can be reduced to 40 mg AZD9291 once daily under circumstances described in Section 6.7. Further dose reductions are not possible. Once a dose has been reduced, it should not be re-escalated at future cycles. Any change from dosing schedule, dose interruptions, or dose reductions should be recorded.

7.3 Labelling

Labels will be prepared in accordance with Good Manufacturing Practice (GMP) and local regulatory guidelines. The labels will fulfil GMP Annex 13 requirements for labelling.

7.4 Storage

All study drugs should be kept in a secure place under appropriate storage conditions. The investigational product label on the bottle and the Investigator Brochure specifies the appropriate storage.

7.5 Compliance

The administration of all study drugs (including investigational products) should be recorded in the appropriate sections of the Case Report Form.

7.6 Accountability

The study drug provided for this study will be used only as directed in the study protocol.

The study personnel will account for all study drugs dispensed to and returned from the subject.

7.7 Concomitant and other treatments

Once enrolled all patients must try to avoid concomitant use of medications, herbal supplements and/or ingestion of foods with known potent inhibitors or inducers of CYP3A4 whenever feasible, but patients may receive any medication that is clinically indicated for treatment of adverse events. Such drugs must have been discontinued for an appropriate period before they enter screening and for a period of 3 months after the last dose of AZD9291. All concomitant medications should be captured on the CRF. Guidance on medicines to avoid, medications that require close monitoring and on washout periods is provided (see Appendix A).

If medically feasible, patients taking regular medication, with the exception of potent inhibitors or inducers of CYP3A4 (see above), should be maintained on it throughout the study period. Patients taking concomitant medications whose disposition is dependent upon CYP3A4, and BCRP and which have a narrow therapeutic index should be closely monitored for signs of changed tolerability as a result of increased exposure of the concomitant medication whilst receiving AZD9291. Additionally due to the potential CYP450 and p-glycoprotein induction risk exposure of drug that are metabolized by CYP3A4, CYP1A2 or CYP2C or whose deposition is mediated by p-glycoprotein could also be reduced and should also be monitored for reduction in therapeutic activity (especially those which have narrow therapeutic index). Guidance on medications to avoid, medications that require close monitoring and on washout periods should be provided (see Appendix A)

Patients should be advised of the potential reduction in effectiveness of oral hormonal contraceptives (due to CYP3A4 induction) when used with AZD921. A change to a non-oral method of contraception (e.g. IUS Levonorgestrel Intra Uterine System, Medroxyprogesterone injections), or addition of a barrier method (e.g. condoms, diaphragm) to the primary hormonal method, is recommended prior to the commencement of treatment. Up to 1.5-fold increase in exposure may occur in statin exposure when co administered with AZD9291. It is recommended that the starting and maintenance dose of statins should be as low as possible and should be guided by the statin label. Monitoring of low-density lipoprotein (LDL) cholesterol levels is advised. If the patient experiences any potentially relevant adverse events suggestive of muscle toxicity including unexplained muscle pain, tenderness, or weakness, particularly if accompanied by malaise or fever, the statin should be stopped, creatine kinase (CK) levels should be checked, and any appropriate further management should be taken. Patients taking warfarin should be monitored regularly for changes in prothrombin time or INR.

7.7.1 Other concomitant treatment

Other medication other than that described above, which is considered necessary for the subject's safety and well-being, may be given at the discretion of the Investigator and recorded in the appropriate sections of the Case Report Form.

7.8 Post Study Access to Study Treatment (Not applicable)

8. STATISTICAL ANALYSES BY SPONSOR

8.1 Statistical considerations

- All personnel involved with the analysis of the study will remain blinded until database lock and protocol violators identified.
- Analyses will be performed by the Sponsor or its representatives.
- Refer to SAP for details (if such a document exists and more details will be added).

8.2 Sample size estimate

The primary endpoint of this study is to evaluate the proportion of patients who achieved an objective response as assessed by the investigator according to RECIST version 1.1. Up to 30 patients (withdrawal 10%) will be enrolled and dosed in order to obtain at least 27 evaluable patients according to Simon's minimax two-stage design as follows: objective response, $P_0=0.05$ and $P_1=0.20$; type 1 error 5%, power 80%, and confidence limit 95%; stage 1 (objective response $\geq 1/13$) plus stage 2 (objective response $\geq 4/27$). All data will be presented for the overall full analysis set, and also by cohorts defined by subtypes of EGFR exon 20 insertion mutations (C-helix vs. loop following C-helix). Descriptive statistics will be used for all variables, as appropriate. Continuous variables will be summarised by the number of observations, mean, standard deviation, median, minimum, and maximum. Categorical variables will be summarised by frequency counts and percentages for each category. OS and PFS will be summarized using Kaplan-Meier estimates of the median event time and quartiles together with their 95% confidence intervals.

8.3 Definitions of analysis sets

The full analysis sets will include all subjects who received at least one dose of study treatment (safety) and dose patients with a baseline tumour assessment (efficacy).

8.4 Outcome measures for analyses

Outcome measures for analyses are presented in Section 2.

8.5 Methods for statistical analyses

8.5.1 Analysis of the primary variable (s)

The investigator-assessed objective response will be evaluated according to RECIST version 1.1 including 95% confidence intervals.

8.5.2 Analysis of the secondary variable(s)

PFS will be summarized using Kaplan-Meier estimates of the median time to progression. OS will be summarized using Kaplan-Meier estimates of the median time to death or censoring and quartiles together with their 95% confidence intervals.

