2.2 Secondary objectives

Secondary Objectives Outcome Measure

To evaluate the safety and tolerability of osimertinib AEs/SAEs as defined by NCI CTCAE version 4.0

To evaluate progression-free survival (PFS) PFS as defined by RECIST version 1.1

To evaluate overall survival (OS)

To evaluate the efficacy based on subtypes of EGFR exon 20 insertion mutation

To evaluate PFS based on subtypes of EGFR exon 20 insertion mutation

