6.3.11 Deaths

All deaths that occur during the study, or within the protocol defined 30 day post study follow up period after the administration of the last dose of study treatment, must be reported as follows:

- Death clearly the result of disease progression should be reported to the study monitor at the next monitoring visit and should be documented in the eCRF but should not be reported as an SAE.
- Where death is not due (or not clearly due) to progression of the disease under study, the AE causing the death must be reported to the study monitor as a SAE within 24 hours (see Section 6.3.8 for further details). The report should contain a comment regarding the co involvement of progression of disease, if appropriate, and should assign main and contributory causes of death. This information can be captured in the 'death eCRF'.
- Deaths with an unknown cause should always be reported as a SAE. A post mortem maybe helpful in the assessment of the cause of death, and if performed a copy of the post-mortem results should be forwarded to AstraZeneca within the usual timeframes.

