9.3 Study timetable and end of study

The end of the study is defined as 'the last visit of the last patient undergoing the study'. End of treatment will not occur until the LPLV occurs of the patient who was deriving clinical benefit or when AZD9291 is discontinued. The study is expected to start in Q2 2017 and to end by Q2 2019. The study may be terminated at individual centres if the study procedures are not being performed according to Good Clinical Practice (GCP), or if recruitment is slow. AstraZeneca may also terminate the entire study prematurely if concerns for safety arise within this study or in any other

study with AZD9291.

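### Section 8.5.2 analyses PFS as time to progression and no section makes death a PFS event; followed as written, the PFS median stays the same or rises

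*Combined protocol and SAP*

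**What the plan says.** The section on secondary variables, 8.5.2, gives one sentence to each time-to-event endpoint. For PFS: "PFS will be summarized using Kaplan-Meier estimates of the median time to progression". For OS: "OS will be summarized using Kaplan-Meier estimates of the median time to death or censoring", followed by quartiles and 95% confidence intervals.

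The other relevant places are these:

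- **Section 8.2**, repeated in the synopsis under statistical methods: "OS and PFS will be summarized using Kaplan-Meier estimates of the median event time and quartiles together with their 95% confidence intervals". It does not say what the event is for either endpoint.
- **Section 2.2:** the outcome measure for PFS is "PFS as defined by RECIST version 1.1". The OS objective has no outcome measure beside it.
- **Section 8.4:** "Outcome measures for analyses are presented in Section 2". This sends the reader back to the entries above.
- **Section 5.1** explains how response and progression are categorised and dated under RECIST 1.1. It does not mention death.
- **Section 8.1** refers to an SAP only in case one exists. **Section 8.5.5** marks sensitivity analysis as not applicable, so no second PFS definition is planned.

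**The concern.** PFS normally ends at progression or death, whichever comes first. Time to progression ends at progression only, and a patient who dies first is censored. Section 8.5.2 uses the name of the first and describes the second. Because no other section lists the PFS events, the only event that the plan attaches to PFS is progression.

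Deaths without documented progression are realistic in this trial. Scans are every two cycles and a cycle is 4 weeks, so they are about 2 x 4 = 8 weeks apart. Entry is open to patients with ECOG status 0-2 and a life expectancy of 12 weeks or more, after progression on chemotherapy. A patient can therefore die before the first or second scan. The safety section also provides for such deaths: "Where death is not due (or not clearly due) to progression of the disease under study" opens one of the reporting rules in Section 6.3.11.

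What is at stake is a reported secondary result in an open-label single-arm trial, where the PFS median will be compared informally with other data. PFS by mutation subtype, also a secondary objective, rests on fewer patients still. If the event is left unsettled, it may be chosen after the data have been seen.

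**Working it through.** **1. The plan's own figure.** No figure is given for PFS or OS. The only sizing statement is the Simon minimax design for response: at least 1 response in 13, then at least 4 in 27, with P0 = 0.05 and P1 = 0.20. The exact binomial probability of passing both stages is 0.0416 at 0.05 (limit 5%) and 0.8011 at 0.20 (target 80%). Enrolment is 27/(1 - 0.10) = 30. The design reproduces and does not depend on how PFS is defined.

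**2. Direction.** Keep every patient's time fixed and change only the label of a death without progression, from event to censored at the date of death. The Kaplan-Meier curve then loses a downward step and never gains one. It lies on or above the PFS curve throughout, so its median is equal or later. The plan states no censoring date. If these patients were instead censored back at their last scan, they would leave the risk set earlier, and the ordering would not be guaranteed in a small sample.

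**3. Size.** Let progression have constant hazard a and death without progression constant hazard b.

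- PFS median = ln 2/(a + b)
- Share of PFS events that are such deaths: d = b/(a + b)
- Median with deaths censored = ln 2/a = ln 2/[(a + b)(1 - d)]
- Ratio of the two medians = 1/(1 - d)

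The documents give neither d nor a PFS median, so both are assumptions. A true median of 4.0 months is used only as an illustration.

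| d | 1/(1 - d) | Change | A true 4.0 months would read |
|---|---|---|---|
| 0% | 1.00 | 0% | 4.0 |
| 5% | 1.05 | +5% | 4.2 |
| 10% | 1.11 | +11% | 4.4 |
| 20% | 1.25 | +25% | 5.0 |
| 30% | 1.43 | +43% | 5.7 |

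If all 27 evaluable patients had a PFS event, d = 10% would be about 3 deaths (0.10 x 27 = 2.7) and d = 20% about 5 (0.20 x 27 = 5.4).

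**4. At the trial's sample size.** With n = 27, a true median of 4.0 months, complete follow-up and 4,000 simulated trials per setting, the median with deaths censored was never below the PFS median. It was strictly higher in 75% of trials at d = 10% and in 95% at d = 20%.

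**The case against.** The strongest reply is that the endpoint is named progression-free survival throughout, so the phrase in 8.5.2 is shorthand and any competent analyst would count deaths. The synopsis and Section 8.2 speak of event time, which fits that reading, and no section says outright that deaths are to be censored. This stands in part: censoring of deaths follows from the stated event and is not a separate instruction. But the general wording in 8.2 names no event, so it cannot correct the one place that does.

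It is also fair that the size is uncertain. If nobody dies without documented progression there is no bias. The 1/(1 - d) formula takes the two hazards as independent, so it does not measure any further distortion if the patients who die are those who were closest to progressing.

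A reader might go further and infer that OS is understated, because "OS will be summarized using Kaplan-Meier estimates of the median time to death or censoring" appears to make censoring an event. The documents do not support that. Beside a named Kaplan-Meier analysis, the phrase is probably loose wording for the observed time, and a censoring time is not the event time that 8.2 calls for. Any figure would also rest on assumed accrual. The plan says only that "The study is expected to start in Q2 2017 and to end by Q2 2019". Taking a 24-month cut-off, an assumed true OS median of 12 months and censoring counted as an event, the median would read 8.9 months with 18-month uniform accrual, but 12.0 months, no change, with 12-month accrual.

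**Conclusion.** The point holds for PFS. Section 8.5.2 states a rule for a different endpoint, and nothing elsewhere makes death a PFS event. With deaths censored when they occur, the direction is certain: the median is the same or higher. The size is an assumption-based range, from no change at d = 0 to +43% at d = 30%, under constant and independent hazards.

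For OS only the wording needs alignment, and no bias is claimed. Nor should the point be read as showing that the plan's conclusion on activity is at risk. PFS and OS are secondary and descriptive, with no test or threshold attached, and the response decision and the sample size do not depend on them. The change should be made before the data are analysed, but it does not affect the design.

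**What to change.** In Section 8.5.2, define PFS as time from first dose to RECIST 1.1 progression or death from any cause, whichever comes first. Censor patients who are alive and progression-free at their last evaluable tumour assessment. First dose is a proposed origin, since the protocol states none; it matches Section 5.1, which times scans from the start of treatment. Time to progression can be kept as a supportive analysis under its own name.

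As a wording alignment, define OS as time from first dose to death from any cause, with living patients censored at the date last known alive. Then bring 8.5.2 into line with the synopsis and Section 8.2, including quartiles and 95% confidence intervals for PFS, which 8.5.2 attaches only to OS. Enter both definitions as outcome measures in Section 2.2, since 8.4 points there.

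The cost is a few sentences and no extra patients. Section 6.3.11 already requires deaths during the study and the 30-day follow-up to be reported. The OS wording does need a source for the date last known alive: Section 4.3 describes a visit 30 days after the last dose and no survival follow-up schedule, so the text should say how survival status is obtained after that visit.
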